### **1.2.2 Treatment response in malignant primary brain tumours**

Primary brain tumours have a 5-year survival rate of only 12%, and GBM has a median survival of 15 months with aggressive multimodal treatment (5). However, there is some evidence to support use of combined chemotherapy in newly diagnosed patients with GBM, uncertainty about chemotherapy regimen choice in grade 2 and 3 gliomas, and uncertainty about therapy choice at relapse across all gliomas.

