## 2.3 Exploratory objectives and endpoints

Tertiary objectives	Endpoints
---------------------	-----------

Determine the rate of successfully established cultures from surgical samples	The percentage of cultures in which $\geq 70\%$ of viable tumour cells encapsulated post-isolation on day 0 are still alive on day 3 in the control cultures (no treatment) compared to the number of tumour samples ( $\geq 0.4g$ ) successfully accepted at Pear Bio's lab.
Determine the rate of successfully cultured immune cells	The percentage of cultures in which $\geq 70\%$ of viable immune cells plated post-extraction on day 0 are still alive on day 3 in the control cultures (no treatment) compared to the number of blood samples ( $\geq 40mL$ ) successfully accepted at Pear Bio's lab.
Find correlations between ex vivo tumour culture or multi-omic biomarkers and real-world patient outcomes	For any cases where patient outcomes are available or become available prospectively, such as recurrence post-surgery, potential predictive or prognostic biomarkers will be identified. As this data will be sparse, the analysis will only be used to generate hypotheses for future trials, if the data allows.
Assess Pear Bio's assay ability to categorise patients for below average or above average overall survival (OS)	
Patient data is collected up to death and their time from diagnosis to death is recorded to determine the overall survival (OS) time.
 
This analysis will use median OS within the study cohort to differentiate patients as generally responsive or resistant to treatment. The analysis will then explore indicators/biomarkers in Pear Bio's test that can identify patients as generally responsive or resistant to treatment, agnostic of the therapeutic choice.

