**Table 1: Schedule of assessments**

Table notes:

1. A redacted histopathology report will be sent to Pear Bio when it is ready (i.e., it does not have to be sent alongside the tissue, blood and other available data from the day of the surgery).
2. Available data is transferred alongside the tumour sample within 24 hours of surgery to Pear Bio's laboratory. Any remaining data will be transferred as soon as feasible, and we will transfer any further imaging at a single timepoint at 12 months after surgery
3. Relating only to research procedures (e.g., taking a volume of blood that is beyond standard care for a given patient). This can be conducted by telephone – physical examination to be done only if clinically indicated.
4. Collected only if available for consenting patients within the study period.
5. Collected only if available for consenting patients within the study period.

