## **7.4 End of study definition**

The end of the trial is defined as the last patient's last data at a maximum of 12 months post-surgery (outstanding data sent to Pear Bio or final laboratory readout, whichever happens later). In cases of early termination of the trial (e.g., due to slow accrual) or a temporary halt, the Sponsor will notify the REC within 15 days of the decision, and a detailed written explanation for the termination/halt will be given.

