## **7.5 Handling of missing data**

Missing data will be recorded as not available on eCRFs. Missing data points will not be imputed in the analysis for that specific endpoint.

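### OS is split at the cohort median with no rule for patients alive at close; the information lost ranges from about a fifth to most of it, depending on follow-up the plan leaves unsettled

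*Combined protocol and SAP*

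**What the plan says.** The OS row of Section 2.3 defines the outcome by death alone: "their time from diagnosis to death is recorded to determine the overall survival (OS) time". It then sets the analysis: "This analysis will use median OS within the study cohort to differentiate patients as generally responsive or resistant to treatment". Assay indicators of that two-level label are sought, whatever treatment was given.

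On follow-up, the same row says "Patient data is collected up to death". Section 7.4 ends the trial at the last patient's "last data at a maximum of 12 months post-surgery". Table 1 has no survival row. Its notes on recurrence follow-up and further therapy read "Collected only if available for consenting patients within the study period", and Section 3.3 lists follow-up outcome data as collected if available.

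On expected survival, Section 1.2.2 says "GBM has a median survival of 15 months with aggressive multimodal treatment" and gives 12% five-year survival for primary brain tumours overall. Section 4.1 also admits grade 1–3 tumours and grade 2–3 meningioma.

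On patients without an event, Section 7.5 says "Missing data points will not be imputed in the analysis for that specific endpoint". No censoring rule, method for estimating the median, or landmark time is given for OS. Section 7.2.3 has only a general paragraph on real-world outcomes and no OS method.

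**The concern.** A patient alive at close has no diagnosis-to-death time, and the plan does not say which side of the median that patient falls on. There are two natural ways to fill the gap.

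- **Deaths only.** The median is taken among patients who died. The longest survivors leave the analysis, and the responsive group becomes those who died somewhat later within the window.
- **Kaplan-Meier median.** Patients seen beyond the median are placed above it. Patients censored before it belong to neither group, and if the median is not reached nobody can be labelled above it.

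Even with every death observed, a two-way cut discards the order of deaths within each half. At stake is the quality of the hypotheses this row is meant to generate.

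**Working it through.** **Inputs from the documents.** At most 50 evaluable patients (Sections 3.7 and 7.1); glioblastoma median 15 months and 12% five-year survival (Section 1.2.2); last data at most 12 months after surgery (Section 7.4). The plan states no power, effect size or number of deaths, so there is no figure of its own to reproduce.

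**Assumptions.** Exponential survival counted from surgery; uniform accrual over 12 or 24 months with everyone followed to close, or a flat 12-month cap per patient; a continuous marker with hazard ratio 1.75 per SD; two-sided 5% tests. Two longer cohort medians were tried:
- 19.6 months, implied by 12% at five years: 60 × ln 2 / (−ln 0.12) = 19.6.
- 30 months, an illustration of a lower-grade mix. It implies 0.5^(60/30) = 25% alive at five years, about twice the protocol's figure.

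**Step 1: alive at close, 15-month median.**
- 12-month cap: 0.5^(12/15) = 0.574.
- Accrual over A months: [15 / (A ln 2)] × [0.5^(12/15) − 0.5^((12+A)/15)].
- A = 12: 1.803 × (0.574 − 0.330) = 0.44.
- A = 24: 0.902 × (0.574 − 0.189) = 0.35.

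**Step 2: who can be placed by a Kaplan-Meier median.**
- Under the cap, the median is reached only if at least 25 of 50 die within 12 months. With death probability 0.426 (15-month median) the binomial chance is 18%. With 1 − 0.12^(1/5) = 0.346 (19.6-month median) it is 1.8%.
- With follow-up to close and a 15-month median, the unplaced are those alive with under 15 months of follow-up. For 12-month accrual, 3/12 of patients have under 15 months, and on average 0.536 of them are alive: 0.25 × 0.536 = 0.13, so 87% are placed. For 24-month accrual, 0.125 × 0.536 = 0.07, so 93% are placed.
- At a 19.6-month median the shares placed are 64% and 82%.

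**Step 3: what a deaths-only median would be.** If a proportion D has died by close, the median death time t satisfies 1 − 0.5^(t/15) = D/2 (valid for t below 12 months). D = 0.426 gives about 5 months, D = 0.56 about 7, and D = 0.65 about 8.5, against a true median of 15.

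**Step 4: simulated power, n = 50, hazard ratio 1.75 per SD.** Figures carry simulation error of a few points.

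| Cohort median; follow-up | Cox, all patients | Kaplan-Meier split | Deaths-only split |
|---|---|---|---|
| 15 mo; 12-month cap | 69% | 15% | 7% |
| 15 mo; 12-month accrual | 81% | 62% | 10% |
| 15 mo; 24-month accrual | 86% | 69% | 14% |
| 19.6 mo; 12-month accrual | 75% | 38% | 9% |
| 19.6 mo; 24-month accrual | 79% | 57% | 11% |
| 30 mo; 12-month accrual | 62% | 8% | 7% |
| 30 mo; 24-month accrual | 71% | 27% | 8% |

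Relative loss with the Kaplan-Meier split:
- 15 months with accrual: 1 − 62/81 = 23% and 1 − 69/86 = 20%.
- 19.6 months: 1 − 38/75 = 49% and 1 − 57/79 = 28%.
- 15 months with the cap: 1 − 15/69 = 78%.
- 30 months: 1 − 8/62 = 87% and 1 − 27/71 = 62%.

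The Kaplan-Meier median was not reached in 76% of runs under the cap (15 months), and in about 75% and 32% of runs at 30 months with 12 and 24 months' accrual.

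**Step 5: cross-check with a 50:50 binary marker and log-rank test.** At hazard ratios 2 and 2.5, the deaths-only split had 5–10% power in every scenario, against 18–72% for log-rank on the same data. With every death observed, the cut alone still cost about a fifth to a quarter: 50% against 66%, and 70% against 87%.

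**The case against.** The strongest reply is that this is a tertiary, hypothesis-generating item. Section 7.1 says the study is not formally powered, and Section 1.1 rules out formal analysis of patient outcomes. That stands and limits the consequence. It does not answer the comparison, which sets two analyses of the same data side by side and needs no claim of adequate power. The Cox analysis is not well powered either: at a hazard ratio of 2 for a balanced binary marker, 80% power needs 66 deaths, more than the 50 patients.

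Several stronger readings are tempting and are not supported.

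- A reader might infer that most of the power is lost whatever happens. At the protocol's 15-month median with 12–24 months' accrual and follow-up to close, a Kaplan-Meier split loses only about a fifth to a quarter.
- A reader might infer that deaths-only is the plan. Section 7.5 bars imputation but does not say survivors are excluded, and placing someone above the median needs only survival past it. Section 2.2 already plans Kaplan-Meier curves for PFS. Deaths-only is one possible reading of a silent text.
- A reader might infer that the result holds for any time origin. All runs start at surgery. The plan counts from diagnosis and admits relapsed patients, whose time before entry was not modelled.
- A reader might infer that markers from this split go straight into later trials, or that real markers would be missed altogether. Nothing says so, and other rows of Section 2.3 relate biomarkers to outcomes without this split.

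Finally, taken at face value, follow-up to death would give every patient an OS value. It conflicts with Section 7.4, and even then the cut alone has a cost (Step 5).

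**Conclusion.** The point holds in conditional form. The plan specifies a median split of a time-to-event outcome, gives no rule for patients alive at close, and contradicts itself on how long patients are followed. On the protocol's glioblastoma figure, roughly a third to over half of patients may be alive at close.

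The size of the loss turns on two things the plan does not state: how survivors are handled, and how long early patients are followed beyond 12 months. It is near total if only deaths count. It is modest with a Kaplan-Meier median, a 15-month cohort and follow-up to close. It is about half at 19.6 months with 12 months' accrual, and most of the power under a 12-month cap or a much longer median. In every scenario run, the censored analysis did better than either split.

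These sizes rest on exponential survival from surgery, the assumed accrual periods and the chosen hazard ratio. Accrual and case mix are not in the documents. The primary laboratory analysis is untouched.

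**What to change.** 1. Reconcile the Section 2.3 statement on follow-up to death with the end-of-study definition in Section 7.4, and state how long survival status is collected for patients who enter early.
2. In Section 2.3, and in Section 7.2.3 where this analysis should be listed, state that OS is analysed as censored time-to-event data: patients alive are censored at the last-known-alive date, and all evaluable patients are kept.
3. Enter each assay marker as a continuous variable in an exploratory Cox model, reporting the hazard ratio per SD with 95% CI and a concordance index.
4. To keep the below/above-average objective, show Kaplan-Meier curves or a descriptive display at the Kaplan-Meier median, with the number of unclassifiable patients reported. Do not fit markers to the binary label.

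The cost is a wording change in two sections and one date field, filled at study close from routine records. No extra patients, visits or procedures are needed. The small downside is that results appear as hazard ratios instead of a simple two-group label.

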### 3: INVESTIGATIONAL PLAN

[figure not shown]
#### 3.1 Overall design

PEAR-GLIO Protocol v1.0  
3rd March 2023

This is a UK-based, observational study that aims to validate a diagnostic tool on its ability to test therapeutic sensitivity of primary solid brain tumours *ex vivo*. Patients diagnosed with a brain tumour on imaging, or who have had previous treatment for a brain tumour and are now undergoing further surgery as clinically indicated, will undergo standard of care surgery, and have 40mL of whole blood collected. The material available from the surgical sample for this study will be shipped fresh alongside whole blood to Pear Bio. The patient will go through routine post-surgical care and data collection. Any previous or subsequent treatments and events occurring post-surgery, such as the administration of adjuvant therapy or recurrence, will be recorded and communicated to Pear Bio. The samples and data sent to Pear Bio will be used to evaluate the study's objectives.

### 3.2 Trial schema

Figure 1: Trial schema

### 3.3 Data and tissue collected

	Biospecimens	Data
Required	
 
At least 0.4g of fresh, unfixed, tumour tissue taken from surgery
 
4 x 10mL EDTA vials of matched whole blood
 
	
 
Demographic data (pseudonymised)
 
Redacted pathology reports, including immunohistochemistry tests, molecular pathology and NGS (IDH and MGMT in particular) and further genomic data where available, including methylation profiling
 

		
 
3. Radiology images and reports
 
4. Concomitant medications
 

Collected if available	N/A	
 
1. Blood and liver/kidney function tests at baseline
 
2. Follow-up outcome data, including recurrences
 
3. Follow-up treatment data, including adjuvant therapy regimens
 

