## 2.2 Secondary objectives and endpoints

Secondary objectives	Endpoints

Assess the accuracy of Pear Bio's assay at correlating to patient progression free survival (PFS)
	
Tumour response will be measured as clinically indicated (typically every 3 months), and at all subsequent timepoints until disease progression, as per standard of care.
 
Disease progression is evaluated by the patient's radiologist and is defined by RANO guidelines.
 
Kaplan–Meier curves will be generated on the patient population, and where feasible, based on their line of treatment and for each therapeutic option (if n is sufficient). These curves will be compared to reported data to determine how representative the patient population is of past trials and clinical practice.
 
Computer vision biomarkers will be categorised into low/high groups to determine their correlation with PFS. This analysis will not demonstrate the patient benefit of using Pear Bio's tool, but it will generate hypotheses for interventional trials designed to demonstrate patient benefit.

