### **5.5.6 Tumour size evaluation**

PEAR-GLIO Protocol v1.0  
3rd March 2023

Measurements will be made by contrast-enhanced MRI. Imaging reports and pseudonymised images will be included as study data collected and transferred to Pear Bio, provided the imaging was done within the period of 3 months prior to surgery or during the follow-up period. Sites will transfer initial imaging shortly after surgery, and again at a single timepoint 12 months after surgery.

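### Relating the assay to PFS is the only secondary objective in section 2.2, yet recurrence data are collected only if available and no censoring rule is given, so PFS may go unascertained

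*Combined protocol and SAP*

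**What the plan says.** Section 2.2 contains a single secondary objective: how well the assay correlates with PFS. Progression follows RANO and is assessed at routine scans, typically every 3 months. Two uses are planned. The first is Kaplan-Meier curves: "These curves will be compared to reported data to determine how representative the patient population is of past trials and clinical practice". The second is a comparison of low and high computer-vision biomarker groups, of which the section says "it will generate hypotheses for interventional trials designed to demonstrate patient benefit".

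The collection rules differ between sections:

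- Section 3.3 puts "Follow-up outcome data, including recurrences" in the row for items collected if available, not in the Required row. Radiology images and reports are in the Required row, without stated timing.
- Table 1, note 4, attached to the follow-up assessments for recurrence, reads "Collected only if available for consenting patients within the study period". Note 5 says the same of further therapy.
- Section 3.1 says, without an availability condition, that treatments and events after surgery, recurrence among them, will be recorded and passed to the sponsor. The synopsis limits this to known events.
- Section 5.5.6: "Sites will transfer initial imaging shortly after surgery, and again at a single timepoint 12 months after surgery".
- Section 7.5 has missing data marked as not available on the eCRF and adds: "Missing data points will not be imputed in the analysis for that specific endpoint". Section 10.2 has monitors pursue missing data unless it is confirmed as not available.

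**The concern.** The endpoint of the only secondary objective in section 2.2 depends on data that the collection table treats as optional. Section 5.5 itemises what sites return. It names no progression status, progression date, date of last progression-free scan or vital status. No section gives a censoring rule or a time origin for PFS, or says how death without documented progression is handled.

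A record with no recurrence report could then mean that the patient had no recurrence, or that nobody looked. If the chance of a report depends on what happened to the patient, both planned uses of PFS suffer. The comparison with reported data is the more exposed, because it reads the level of the curve directly. Analysis cannot recover a status that was never requested.

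**Working it through.** The plan gives no figure to reproduce. Fifty evaluable patients is a maximum (section 7.1), the study is not formally powered, and no event count, dropout rate or missingness rate is stated. Every rate below is an assumption except n = 50 and the 15-month median survival.

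**1. Could the required imaging supply the status?** Only in part. Images show progression in patients who were scanned. They give no status for a patient who deteriorated or died without a further scan, and follow-up images are transferred once, at 12 months. Section 1.2.2 gives a median survival of 15 months for glioblastoma. If survival were exponential (assumed), the proportion dead by 12 months would be 1 − 0.5^(12/15) = 0.43. Deaths before the transfer would therefore be common in that subgroup.

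**2. Only progressions go unrecorded.** Let S be true 12-month PFS and m the fraction of progressors not recorded. Assume S = 0.40.

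- Dropped from the analysis: S / [S + (1 − S)(1 − m)]
- Read as event-free: 1 − (1 − S)(1 − m)

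| m | Dropped | Shift | Read as event-free | Shift |
|---|---|---|---|---|
| 0.2 | 0.40/0.88 = 45.5% | +5.5 | 1 − 0.60 × 0.8 = 52% | +12 |
| 0.4 | 0.40/0.76 = 52.6% | +12.6 | 1 − 0.60 × 0.6 = 64% | +24 |

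Sampling error for comparison: 1.96 × √(0.25/50) = 0.139, about ±14 points. Three of the four shifts are below this; only the +24 exceeds it.

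**3. Both groups can go unrecorded.** Let q1 be the probability of a record given progression and q0 the probability given no progression. Assume S = 0.50. The complete-case estimate is S·q0 / [S·q0 + (1 − S)·q1]; counting the unrecorded as progression-free gives 1 − (1 − S)·q1. The last column comes from a simulation of 200,000 exponential times, with unrecorded patients censored at a uniformly distributed earlier contact.

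| q1 / q0 | Complete-case | Unrecorded read as event-free | Censored at earlier contact |
|---|---|---|---|
| 0.8 / 0.8 | 0.40/0.80 = 50% | 60% | about 53.5% |
| 0.9 / 0.6 | 0.30/0.75 = 40% | 55% | about 46% |
| 0.6 / 0.9 | 0.45/0.75 = 60% | 70% | about 63% |

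Against a true 50%, the complete-case estimate is unbiased, 10 points low or 10 points high, depending only on the assumed pattern. For any one pattern, the choice of handling rule moves the answer by 10 to 15 points, and the plan does not make that choice.

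**The case against.** The strongest reply is that little rests on PFS here. Section 1.1 says patient outcomes will have no formal statistical analysis, section 2.2 presents the PFS work as hypothesis-generating, section 2.3 expects sparse outcome data, and the primary analysis uses no outcomes. Section 7.2.2, headed as the secondary analysis, concerns omics biomarkers against *ex vivo* response and does not mention PFS. Collecting what routine care provides is a common choice in an observational study. This stands, and it limits the importance of the point.

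The plan also has provisions that help. Table 1 makes data transfer study-specific at follow-up visits and at recurrence, radiology is required, section 2.3 speaks of collection up to death, and consent to outcome data is an entry criterion. Sections 7.5 and 10.2 show an intention to mark and chase missing data. The eCRF itself is not among the documents, so it may hold a status field. These provisions narrow the gap without closing it: none asks for a dated status on every patient, and confirming data as unavailable satisfies the monitoring rule.

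A reader might infer that the curves do rest on an outcome-dependent subset and will look too favourable. The documents do not support that. Nothing in them says that availability depends on outcome, and the recurrence column of Table 1 could favour capture of progressions and push the bias downward. Nor does section 7.5 say that patients without outcome data are dropped: it rules out imputation, and Kaplan-Meier can censor without imputing.

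**Conclusion.** The point holds as an internal conflict and an ascertainment gap. Section 3.3 and Table 1 note 4 make recurrence data optional while section 3.1 says they will be recorded, and no listed item or rule fixes each patient's PFS status or censoring date. A site that follows section 3.3 can leave PFS unascertained.

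Bias is possible, but its direction and size are unknown. If only progressions go unrecorded (20% to 40% of them, with true 12-month PFS of 40%), the shift is about 5 to 13 points when those patients are dropped and 12 to 24 points when they are read as event-free, against about ±14 points of sampling error. These rates are assumptions, so the figures show only that the effect could matter. A claim that bias generally exceeds sampling error would go too far. The effect is confined to a hypothesis-generating analysis, chiefly the comparison with reported data; the primary objective is untouched. This is a cheap improvement worth making.

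**What to change.** For every evaluable patient who has not withdrawn consent, move three items to the Required row of section 3.3: progression yes or no with date; date of the last progression-free scan; vital status with date. Return them on one eCRF page, completed from routine notes, at the existing 12-month transfer. Limiting this to evaluable patients leaves out those withdrawn and replaced under sections 5.7 and 3.6, who have no assay result to relate to PFS. The consent exception follows section 5.6.1.

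In section 7, state the PFS time origin, how death without documented progression is treated, and censoring at the last progression-free scan. Report the number of patients without a status, with best- and worst-case bounds. For example, with 20% missing and 50% PFS among the rest, the bounds are 0.8 × 0.5 = 40% and 0.8 × 0.5 + 0.2 = 60%. Censoring alone does not remove bias, as the last column of the second table shows, so the count matters. Align Table 1 note 4 with section 3.1.

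The cost is a small site workload of one page per patient, with no extra visits or scans.
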